Both major and minor events will be reported using the study's Adverse, Unexpected, or Notable Event Reporting Form. Any major related and unexpected event, i.e., any serious injury or life-threatening event, will be reported immediately (within 24 hours of notification) to the WFSM Institutional Review Board (IRB) right after completing any and all actions that are necessary to protect the subject's health and safety. The SAE will also be reported within 24 hours to the NIA and Chair of the DSMB via a verbal phone call, or by a report submitted by fax or email. Minor events will be reported within seven days. A description of the event, and the date and location of the event will be recorded on this form, which will be kept in the subject's research file.

Reporting of Unanticipated Problems, Adverse Events or Deviations

Any unanticipated problems, serious related and unexpected adverse events, deviations or protocol changes will be promptly reported by the principal investigator or designated member of the research team to the IRB and sponsor or appropriate government agency if appropriate.

Use of biological samples by other investigators

Biological samples may be used by investigators other than the investigators of the current study. The use will be limited to non-commercial purposes. The names and other personal identifiers of the study participants will not be sent to any recipients of the blood samples.

Storage and disposal of biological material

Blood and urine samples will be stored at Wake Forest University Medical Center for up to twenty years after the end of the trial at which time the samples will be destroyed. Biological specimens will be stored in locked -70°C alarmed freezers located in a locked room. The Wake Forest Pepper Center Integrative Biology Core lab coordinator ([name]) and the Core Leader ([name]) have access to the keys of the freezers. All the specimens will have numerical study IDs with no personal identifiers of the participants. These are stored under the Pepper Center Tissue Repository (IRB#1219).

Bibliography and References Cited

2. Jensen GL. Obesity and functional decline: epidemiology and geriatric consequences. *Clin.Geriatr Med* 2005 Nov;21(4):677-87, v

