Our **primary goal** is to determine the effect of a higher protein (1.2 g/kg body wt/d; ~30% of energy) / lower carbohydrate (CHO; 40-45% of energy) diet during a 6-month weight loss intervention in obese older adults on physical function compared with an isocaloric lower protein (current RDA of 0.8 g/kg body wt/d; 15-20% of energy) / higher CHO (55-60% of energy) diet, and whether continuing a higher protein / lower CHO diet following weight loss results in better maintenance of physical function. This will be accomplished with an 18-month randomized trial in 225 obese (BMI 30-45 kg/m² or 27-30 kg/m² with 1 additional risk factor), older (65-85 years) men and women at risk for disability (expSPPB <2.50). All participants will undergo a 6-month weight loss intervention of caloric restriction and exercise followed by 12 months of follow-up with randomization to one of three groups (n=75/group): 1) Lower protein / higher CHO diet for the 6-month weight loss and 12-month follow-up phases (RecProt); 2) Higher protein / lower CHO diet for the 6-month weight loss phase only (6-mo HiProt); or 3) Higher protein / lower CHO diet for the 6-month weight loss and 12-month follow-up phases (18-mo HiProt).

Primary Aim: To determine the effects of a higher protein / lower CHO diet vs. lower protein / higher CHO diet during a 6-month weight loss intervention and 12 months of follow-up on 18-month physical function assessed by the expanded Short Physical Performance Battery (primary outcome) and muscle strength.

Hypothesis: Participants randomized to a higher protein diet during weight loss and follow-up (18-mo HiProt) will have greater improvements in physical function than participants randomized to a higher protein diet during weight loss only (6-mo HiProt), followed by those randomized to a lower protein diet (RecProt).

Secondary Aim: To determine the effects of a higher protein / lower CHO diet vs. lower protein / higher CHO diet during a 6-month weight loss intervention and 12 months of follow-up on 18-month body weight and body composition.

Hypothesis: Participants randomized to a higher protein diet during weight loss and follow-up (18-mo HiProt) will have better weight loss maintenance, lower fat-to-lean mass ratio, greater thigh muscle volume, and lower inter-muscular adipose tissue than participants randomized to a higher protein diet during weight loss only (6-mo HiProt), followed by those randomized to a lower protein diet (RecProt).

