We will also assess the effects of a higher protein diet on: 1) 6-month changes in physical function, weight, and body composition; 2) 6- and 18-month changes in bone mineral density; and 3) 6- and 18-month changes in cardiometabolic risk factors (e.g., glucose and lipids); and 4) whether the effects of a higher protein diet on lean mass mediates the effects on physical function at 6- and 18-months.

Methods and Measures

Study Overview:

We will use a 3-group design in 225 obese (BMI 27-30kg/m² with 1 risk factor or BMI 30-45 kg/m²), older (65-79 years) men and women at risk for disability (expSPPB <2.50) who will undergo a 6-month weight loss intervention followed by a 12-month follow-up phase to test our overall hypothesis that a higher protein (1.2 g/kg body wt/d) / lower CHO diet during a 6-month weight loss intervention improves physical function compared with an isocaloric lower protein (the current RDA, 0.8 g/kg body wt/d) / higher CHO diet and continuing a higher protein / lower CHO diet for 12-months following weight loss will result in better maintenance of improved physical function. All participants will undergo a 6-month weight loss intervention involving caloric restriction and supervised exercise followed by 12 months of follow-up with randomization to one of three groups (n=75/group): 1) Lower protein / higher CHO diet for the 6-month weight loss and 12-month follow-up phases (RecProt); 2) Higher protein / lower CHO diet for the 6-month weight loss phase only (6-mo HiProt); or 3) Higher protein / lower CHO diet for the 6-month weight loss and 12-month follow-up phases (18-mo HiProt). Physical function (primary aim) will be assessed by the expanded Short Physical Performance Battery (expSPPB) and muscle strength and body composition (secondary aim) assessed by dual-energy X-ray absorptiometry (DXA) and computed tomography (CT) at baseline, 6- and 18-months. At the same time points, we will also measure bone mineral density (DXA) and cardiometabolic risk factors.

Recruitment of study participants:

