Fasting blood draw						X					X
Anthropometrics		X					X				X
DXA scans		X					X				X
CT scans				X			X				X
CHAMPS physical activity questionnaire						X		X			X
MAT-sf					X		X		X		X
CES-D						X		X			X
SF-36				X			X		X		X
DSST				X			X				X
Fatigue questionnaire (FACIT)				X			X		X		X
Instructions for 24-hr urine sample collection†				X			X				X
Return 24-hr urine sample†					X		X				X

* Expanded SPPB at FV1/2, FV3, and FV4/5 only.

† Collected from ppts after FV1/2; delivered to ppt prior to FV4/5.

** Dropped after COVID19 in-person research pause to allow us to combine FV1 & FV2 visits

*** Dropped after COVID19 in-person research pause to allow us to combine FV4 & FV5 visits

All assessments will take place by study staff blinded to the participant's treatment assignment. To ensure that staff remain blinded, participants will be asked not to discuss their intervention with the assessor. Additionally, the staff member will remind the participants not to tell them which intervention group they have been assigned to.

The first screening visit (SV1) and the resting metabolic rate (RMR; BV2 and FV1/2 (6-mo)) and fasting blood draw visits (BV2, FV1/2 (6-mo), and FV4/5 (18-mo)) will occur in the early morning after an 8 hour fast. After a blood draw for the metabolic screening panel and CBC (SV1), RMR (BV2 and FV1/2), and fasting blood (BV2, FV1/2, and FV4/5), participants will be given a light breakfast. BV1 and BV2 will occur approximately one week apart. The follow-up visits will occur (1) after the 6-month intervention (FV1/2; weeks 27-32), (2) 6 months post-intervention (FV3; weeks 53-56), and (3) 12 months post-intervention (FV4/5; weeks 79-84).

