The **6-month follow-up visit (FV1/2)** will take place following week 26 of the intervention in the morning after an 8 hour overnight fast. Participants will have their weight and blood pressure measured. Then participants will have their resting metabolic rate (RMR) measured for the purpose of estimating each person's weight maintenance calorie level. The participant will also undergo tests to assess arterial stiffness. Blood will be drawn for glucose, insulin, HbA1c, lipids, CMP and CBC, and storage. Participants will then be provided with a snack. Any changes to medical history and current medications and dietary supplements will be reviewed. Whole-body, AP spine, and hip DXA scans will be done. The participant will have anthropometric measurements taken at their waist, hip and thigh. Lower extremity muscle strength (BiodeX dynamometer), grip strength, physical performance (expSPPB), and 400-m walk time will be measured. The MAT-sf and DSST will be administered. The CHAMPS Physical Activity Questionnaire, CES-D, SF-36, and FACIT questionnaires will be administered at the visit time permitting or by phone after the completion of the in-person visit. A series of CT scans (abdomen, hip and thigh) will be done. Participants will be given the 24-hr urine collection bottle and instructions for collecting urine to measure urinary nitrogen and creatinine for estimating dietary protein intake and for storage. Three 24-hr diet recalls will be administered by phone during the FV1/2 visit window. . Participants will schedule to drop off their 24-hour urine sample following their FV1/2 visit

Monthly phone calls: Participants will be called once a month during the 12-mo follow-up to ensure those that are in the 18-mo HiProt are continuing to consume the protein supplement. All participants will be asked about any health changes, injuries, etc., that may have occurred and any events recorded using the Adverse Event Form.

The **12-month follow-up visit (FV3)** will take place following week 52 of the intervention. Participants will have their weight and blood pressure measured. Lower extremity muscle strength, grip strength, physical performance (expSPPB), and 400-m walk time will be measured. The CHAMPS Physical Activity Questionnaire, MAT-sf, CES-D, SF-36, and FACIT questionnaires will be administered. Medical history and current medications and dietary supplements will be reviewed.

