Compliance: During the 6-month weight loss phase, participants will be asked to track their daily intake of all foods and beverages in a log book provided to them and their log books reviewed at each session. Attendance at group and individual diet and exercise sessions and protein supplement usage during the study will also be tracked.

Physical activity: Physical activity will be assessed by self-report at baseline, and at 6-, 12- and 18-month follow-up using the CHAMPS physical activity questionnaire.³²

Dietary intake: Three 24-hr dietary recalls (two week days and one weekend day) will be performed on all participants at baseline, and at 6- and 18-month follow-up. Experienced registered dietitians trained in 24-hr dietary recall interviews from the WFSM Clinical Research Unit (CRU) who are not involved with the diet intervention will conduct the 24-hour dietary recalls. Data will be collected and analyzed using the Nutrition Data System for Research (NDSR) software developed and supported by the Nutrition Coordinating Center at the University of Minnesota. The NDSR database is updated annually to reflect marketplace changes and new analytic data. The program also uses the multiple pass approach, providing interview prompts to guide and standardize data entry, thereby providing multiple opportunities for the participant to recall food intake and improve data accuracy. A validated visual portion guide will be provided to the participant for use in determining accurate portion sizes. During the baseline visit, a CRU dietitian will obtain the first 24-hour recall in person, and this interview will be used to introduce and train the participant for the procedures used in subsequent 24-hr dietary recalls done by phone. The remaining 24-hr dietary recalls will be conducted over the phone (taking approximately 20-40 minutes each) by placing unscheduled telephone calls to participants. When contacted by the staff, participants will be asked to recall and report their dietary intake from the previous day's 24-hour period.

Urinary nitrogen excretion, a biomarker of dietary protein intake,⁶⁰ will be used to verify protein intake between groups. Participants will be asked to collect urine over a 24-hr period at baseline, 6- and 18-month follow-up.

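### The 6-month urine and diet recalls are scheduled after week 26, so for the 6-mo HiProt arm they may not reflect protein intake during the weight-loss phase

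*Protocol*

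**What the plan says.** The protocol's Objectives and Study Overview define the two higher-protein arms by how long the diet lasts: "Higher protein / lower CHO diet for the 6-month weight loss phase only (6-mo HiProt" and "Higher protein / lower CHO diet for the 6-month weight loss and 12-month follow-up phases (18-mo HiProt". RecProt has the lower-protein diet in both phases. Under Macronutrient distribution, every participant starts with enough supplement for six months, and at the end of weight loss only 18-mo HiProt is resupplied.

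On timing, Schedule and organization of assessment visits states: "The follow-up visits will occur (1) after the 6-month intervention (FV1/2; weeks 27-32". The description of the 6-month visit says that it "will take place following week 26 of the intervention in the morning". The urine bottle is handed out at that visit, and "Participants will schedule to drop off their 24-hour urine sample following their FV1/2 visit". The Table 2 footnote agrees: "Collected from ppts after FV1/2; delivered to ppt prior to FV4/5". For diet, "Three 24-hr diet recalls will be administered by phone during the FV1/2 visit window".

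On purpose, the urinary nitrogen paragraph says that the measure "will be used to verify protein intake between groups", with collections at baseline, 6 and 18 months. Recalls are made at the same three time points. Neither is scheduled between baseline and the FV1/2 window.

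**The concern.** A 24-hour urine and a 24-hour recall describe intake around the day they cover. For RecProt and 18-mo HiProt this does no harm, because their assigned protein level is the same before and after week 26. For 6-mo HiProt the assignment changes at the end of weight loss, and both 6-month measures come after that point. The plan therefore has no biomarker or recall that falls clearly inside this arm's higher-protein phase.

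What is at stake is the trial's check of its own contrast. A fully adherent 6-mo HiProt arm could look non-adherent at 6 months. The same values could also enter the process-adjusted analyses that the protocol's Data analysis section says will be considered, where protein intake and urinary nitrogen are named as examples. A low reading taken after the phase would then stand in for a high exposure during it.

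**Working it through.** The plan gives no figure to reproduce here. The check is calendar arithmetic followed by a dilution range.

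**1. Calendar**
- End of weight-loss intervention: about week 26, since FV1/2 follows week 26. FV3, described as six months after the intervention, opens in week 53, and 53 - 27 = 26 weeks after FV1/2 opens, which is consistent.
- FV1/2 window: weeks 27 to 32. 27 - 26 = 1 and 32 - 26 = 6, so the visit falls 1 to 6 weeks after week 26.
- Urine: after FV1/2, so later still.
- Recalls: within the same window. Their order relative to the visit itself is not stated.

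**2. Dilution**

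Let D be the true weight-loss-phase gap in protein intake between a higher-protein arm and RecProt, and let f be the fraction of 6-mo HiProt back at the lower-protein level when sampled. Assume the two HiProt arms are equal in size, both have gap D during weight loss, and 18-mo HiProt still has gap D when sampled. Then:
- measured 6-mo HiProt vs RecProt = (1 - f) x D
- measured pooled HiProt vs RecProt = [(1 - f) x D + D] / 2 = (1 - f/2) x D

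The documents do not give f, so the whole range is shown. For scale, the targets are 1.2 and 0.8 g/kg/d, a difference of 0.4 g/kg/d. At an assumed 90 kg, D = 0.4 x 90 = 36 g/d.

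| f | 6-mo HiProt vs RecProt | Pooled HiProt vs RecProt |
|---|---|---|
| 0 | 100% (36 g/d) | 100% (36 g/d) |
| 0.25 | 75% (27 g/d) | 87.5% (31.5 g/d) |
| 0.5 | 50% (18 g/d) | 75% (27 g/d) |
| 0.75 | 25% (9 g/d) | 62.5% (22.5 g/d) |
| 1 | 0% (0 g/d) | 50% (18 g/d) |

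Varying the assumed weight from 80 to 110 kg changes D from 32 to 44 g/d, and the pooled value at f = 1 from 16 to 22 g/d. The percentages do not change.

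**3. What is not affected**
- 18-mo HiProt vs RecProt: the assigned contrast is the same on both sides of week 26. The two HiProt arms share one assignment during weight loss, so this comparison is a reasonable randomised proxy for the phase.
- Food logs reviewed at each session and supplement tracking (Compliance) cover weight loss in every arm, although neither is a biomarker.

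**4. Where the documents leave the stop point open**
- Macronutrient distribution and the 12-month follow-up paragraph tie the resupply and the maintenance plan to the end of the weight-loss intervention, without naming a week.
- The 6-month visit description and the resting metabolic rate paragraph use the metabolic rate measured at FV1/2 to set maintenance calories, which points to a change at or after that visit.

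These sections do not fix one date, relative to the urine and recalls, on which 6-mo HiProt's assigned diet ends.

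**The case against.** The strongest reply is that no section dates the switch. If maintenance calories are set from the FV1/2 metabolic rate, participants may stay on the assigned diet until that visit, and recalls made earlier in the window could still catch it. This stands as a reason not to assume f = 1. It helps the recalls more than the urine, which follows the visit. It also concerns calories rather than the protein assignment, which the Objectives limit to the weight-loss phase.

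A reader might infer that the 6-month measures cannot verify the weight-loss contrast at all, or that the measured contrast will be halved. The documents do not support either. The first overlooks 18-mo HiProt vs RecProt, the logs and the supplement tracking. The second requires the whole arm to be back at RecProt's level when sampled, and no section assigns 6-mo HiProt 0.8 g/kg/d in follow-up. Zero and one half are the lower bounds of the range.

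Two further points stand. The process-adjusted analyses are optional, and the SAP mentions neither urinary nitrogen nor recalls. The SAP does pool 120 higher-protein against 60 lower-protein participants at 6 months, but for bone outcomes; no document pools the arms for the intake check.

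Finally, the 18-month urine is not a model of in-phase timing. Its bottle goes out before FV4/5, but that visit is in weeks 79-84, after week 78. It shows only that delivery before a visit is workable.

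**Conclusion.** The concern holds in a limited form. Both 6-month intake measures are scheduled after week 26, and the urine after the FV1/2 visit itself. For 6-mo HiProt, whose higher-protein assignment and powder supply cover weight loss only, they may not reflect weight-loss-phase intake. Depending on f, the measured gap to RecProt lies between 100% and 0% of the true gap, and a pooled HiProt gap between 100% and 50%. The range rests on the equal-arm and equal-gap assumptions stated above and on switchers returning to RecProt's level.

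The 18-mo HiProt vs RecProt check keeps its assigned contrast, and no primary or secondary outcome estimate depends on these values. The weakness is in verifying adherence and in any protein-adjusted secondary analysis. It is worth correcting because the correction is cheap.

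**What to change.** 1. **Reconcile the text.** Macronutrient distribution, the 12-month follow-up paragraph, the visit schedule with Table 2, the 6-month visit description and the resting metabolic rate paragraph should agree on when 6-mo HiProt's assigned diet ends relative to the 6-month urine and recalls.
2. **Remaining collections, if any.** Deliver the bottle and make the three recalls in the last weeks of the intervention, before week 26 ends, with the urine returned at FV1/2. This moves an existing procedure a few weeks earlier. The protocol already reports actual enrolment (187) and the SAP is dated 04/24/2023, so few or none may remain.
3. **Samples already collected.** Record each collection date relative to week 26 and to the end of the assigned diet. Base the biomarker check of the weight-loss phase on 18-mo HiProt vs RecProt, and use logs and supplement tracking for 6-mo HiProt.
4. **Protein-adjusted analyses.** Do not use 6-mo HiProt values collected after its higher-protein assignment ended as that arm's weight-loss-phase exposure. Values shown to fall within the assignment can stay.

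The cost is that the biomarker check from existing samples rests on two arms, and protein-adjusted analyses lose the 6-month urine and recall exposure for the affected 6-mo HiProt participants, possibly the whole arm.
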